11.1.2 Treatment-Emergent Adverse Event

A TEAE is any event not present before administration of study drug or any event that was already present but worsens in either intensity or frequency following exposure to the study drug.

Serious Adverse Event

An AE is considered “serious” if, in the view of either the investigator or Acer, it results in any of the following outcomes:

- Death
- Is immediately life threatening
- Requires in-patient hospitalization or prolongation of existing hospitalization
- Results in persistent or significant disability or incapacity
- Results in a congenital abnormality or birth defect
- Is an important medical event that may jeopardize the subject or may require medical intervention to prevent one of the outcomes listed above

Events not considered to be SAEs are hospitalizations for:

- Routine monitoring of the studied indication and not associated with any deterioration in condition or AE
- Elective treatment for a pre-existing condition that did not worsen
- Respite care or observation when there is no AE associated with the hospitalization

11.2 Reporting of Adverse Events and Serious Adverse Events

11.2.1 Reporting of Adverse Events

All AE data will be collected from the time that signed informed consent is obtained until the subject fully completes her/his study participation of the study. Ongoing AEs will be monitored (telephone call) until resolution or for 30 days, whichever is first.

Abnormal lab findings will be closely monitored by the Sponsor and repeated as deemed necessary until resolution and followed up by the treating physician. All safety data will be reviewed by the Sponsor for any potential safety signals that would alter the safety profile of the molecule.

All AEs, whether assessed by the investigator to be related or unrelated to the study drug, must be documented in the subject's medical records, in accordance with the investigator's normal clinical practice and on the AE electronic case report form (eCRF). Each AE is to be evaluated for duration, intensity, frequency, seriousness, outcome, other actions taken, and relationship to the investigational product.

11.2.2 Reporting of Serious Adverse Events

In agreeing to the provisions of this protocol, the investigator accepts all legal responsibilities for immediate reporting of SAEs to Acer.

Any SAE, whether or not considered related to study drug, will also be reported immediately (within 24 hours) to Acer or the Acer designee Drug Safety Department by email ([contact]) using the study-specific SAE Report Form and will be entered into the EDC system within 24 hours. A study-specific SAE report form (paper) will be used if the EDC system is not available.

The reporting period for SAEs is the period from the time of check-in through check-out and within 30 days after the last dose of study drug.

Any medication or other therapeutic measures used to treat the event will be recorded on the appropriate eCRF page in addition to the outcome of the SAE. Investigators should not wait to collect additional information that fully documents the event before notifying Acer or the Acer

designee Drug Safety Department of an SAE. Acer or the Acer designee may be required to report certain SAEs to regulatory authorities within 7 calendar days of being notified about the event; therefore, it is important that investigators submit additional information requested by Acer or the Acer designee as soon as it becomes available.

Reporting of SAEs to the institutional review board (IRB) will be conducted in accordance with the SOPs and policies of the IRB. Adequate documentation must be provided to Acer or the Acer designee showing that the IRB was properly notified.

All SAEs must be reported to Acer. SAEs are reported by entering the SAE data into the study specific EDC system. Entering the SAE data into the EDC system will automatically notify Acer of the event. If an SAE occurs in a subject during the study, in the event the EDC system is inaccessible, the following Acer personnel is to be contacted:

[name]
[contact]
[contact]
Email: [contact]

If an SAE is reported by telephone, an SAE Report Form must also be completed in the EDC system as soon as the EDC system is accessible. At a minimum, the following information should be provided at the time of the initial report:

- Subject number
- Event term
- At least 1 criterion classifying the event as serious
- Name and title of the reporting individual
- Causal relationship to the investigational product

The investigator will assess whether the event is causally related to the investigational product. Acer will also assess whether the event is causally related to the investigational product, in addition to assessing the overall safety profile of the investigational product. Acer will notify the appropriate regulatory agencies of expedited safety reports that occur during the study within the time frames required by each regulatory agency.

An SAE assessed with a possible, probable, or definite causal relationship to the investigational product and unexpected according to the IB, is known as a suspected unexpected serious adverse reaction (SUSAR) and will be expeditiously reported to regulatory authorities and investigators, as appropriate.

Following the initial report, any additional information obtained by the investigator about the SAE must be reported promptly to Acer in the same manner as described above for the initial SAE report. Any supporting source documentation should be emailed to [contact] as soon as possible.

The investigator is responsible for submitting information on expedited safety reports received from Acer to their local IRB, as directed by the local-country requirements.

Documentation of the submissions to IRBs must be retained in the appropriate study files. As instructed by Acer, expedited safety reports should be retained in the appropriate investigative site study files, or with the IB.

11.2.3 Additional Investigator Responsibilities for Serious Adverse Events

The safety data recorded in the EDC represent the official record of all Aes and SAEs reported in the study. The investigator should comply with requests by the medical monitor or other Acer personnel to record the SAE on the subject's AE EDC. Other supporting documents such as radiology reports, hospital discharge summaries, and autopsy reports should also be provided, when appropriate. Additionally, upon request by Acer, the investigator should provide input into the SAE narrative and provide timely information to ensure prompt follow-up and closure of the SAE report.

The investigator and supporting personnel responsible for subject care should discuss with the medical monitor any need for supplemental investigations of SAEs. The results of these additional assessments must be reported to the medical monitor.

11.2.4 Notification of Post-Study Serious Adverse Events

If an investigator becomes aware of an SAE that may be attributable to the investigational product at any time after the end of the study, Acer should be notified immediately (i.e., within 24 hours).

All SAEs that occur within 30 days following the cessation of investigational product, whether or not they are related to the study, must be reported to Acer within 24 hours.

11.2.5 Follow-Up of Adverse Events and Serious Adverse Events

All Aes must be followed during the study until the AE resolves, is no longer of clinical concern, has stabilized or is otherwise explained, or the subject is lost to follow-up. Ongoing Aes will be monitored (telephone call) until resolution or for 30 days, whichever is first.

Abnormal lab findings will be closely monitored by the Sponsor and repeated as deemed necessary until resolution and followed up by the treating physician. All safety data will be reviewed by the Sponsor for any potential safety signals that would alter the safety profile of the molecule.

Any Aes ongoing at the final visit that are deemed to be possibly, probably, or definitely related to the investigational product or of other clinical significance must be followed for as long as necessary to adequately evaluate the safety of the subject or until the event stabilizes, resolves, or is no longer of clinical concern. If resolved, a resolution date for the AE should be documented on the eCRF. The investigator must ensure that follow-up includes any supplemental investigations indicated to elucidate the nature and/or causality of the AE. This may include additional laboratory tests or investigations or consultation with other healthcare professionals, as considered clinically appropriate, by the investigator.

11.2.6 Pregnancy and Follow-Up

Pregnancies are not considered Aes in and of themselves; however, if a female subject becomes pregnant while she is enrolled in the clinical study, she must interrupt/discontinue investigational product immediately and Acer must be notified within 24 hours of the investigator learning of the pregnancy by completing the pregnancy follow-up section in the EDC. Entering the pregnancy report into the EDC system will automatically notify Acer of the pregnancy.

In the situation that the EDC is not functioning, the medical monitor should be notified by telephone and a pregnancy notification form may be emailed to Acer at [contact]. The investigator remains responsible for entering the pregnancy information into the EDC when the EDC becomes functional.

The subject and neonate must be followed for outcome information and/or as considered appropriate by the investigator and Acer. The investigator should notify Acer of the outcome of the pregnancy by completing pregnancy follow-up section in the EDC. In the situation that the EDC is no longer available due to study closure, a pregnancy outcome form should be completed and faxed or emailed to Acer. Thereafter, the subject and infant must be followed as considered appropriate by the investigator and Acer.

Completing the pregnancy report in the EDC is not a substitute for reporting an AE/SAE when an AE/SAE has occurred. In the situation when an AE/SAE has occurred, the AE/SAE reporting procedures described in [Section 11.2](#) must also be followed.

11.3 Other Safety Parameters

11.3.1 Medical History

A complete medical history will be obtained from the subject at screening ([Table 1](#)). Demographic characteristics (age, sex, race, and ethnicity) will also be recorded.

Medical history will include specific information relating to any prior or existing medical conditions or surgical procedures involving the following systems: general appearance; dermatologic; head, eyes, ears, nose, and throat (HEENT); lymphatic; cardiovascular; respiratory; gastrointestinal; genitourinary; musculoskeletal; and neurological. A history of alcohol or drug abuse in the previous 6 months will be collected.

Investigators will query subjects for smoking and tobacco use history. Investigators will also query subjects regarding current alcohol intake (i.e., number of drinks per day).

11.3.2 Vital Signs, Height, and Weight

To monitor subject safety, heart rate, blood pressure, body temperature, pulse oximetry, and respiratory rate will be measured for each subject as indicated in Table 1. Vital signs will be measured while subjects are in a sitting position and standing position.

The minimal positional time for collection of the orthostatic vital signs is approximately 5 minutes sitting and approximately 2 minutes standing prior to collection of vital signs.

When the time of vital signs monitoring coincides with a blood draw, vital signs will be taken within approximately 10 minutes of the scheduled blood draw and 60 minutes prior to the morning dose. Vital signs may be taken at other times if deemed necessary. Height and weight will be measured at screening to calculate BMI.

11.3.3 Concomitant Medications

All prescription and over-the-counter medications taken by a subject during the 30-day period before screening will be recorded at screening. All medications taken by subjects during the study will also be recorded. If drug therapy other than that specified in this protocol is required, a

decision to continue or discontinue the subject from the study will be made by the investigator, based on the time the medication was administered and its pharmacology and PK. Any concomitant medications added or discontinued will be recorded at screening and throughout the study ([Table 1](#)).

11.3.4 Physical Examination

Physical examinations will be performed for each subject as indicated in Table 1, and can be performed at other times, if deemed necessary. A full physical exam may include, but is not limited to evaluation of general appearance, cardiovascular and respiratory system, upper and lower extremities, genitourinary system, abdominal examination, HEENT, and a general neurologic physical exam. Assessment of other systems may be conducted as clinically indicated.

11.3.5 Safety Electrocardiogram

A 12-lead safety ECG (after 5 minutes in supine position) will be performed for each subject as indicated in Table 1 and can be performed at other times, if deemed necessary. The ECG readings will be performed approximately 1 hour after the scheduled morning dose on dosing days.

11.3.6 Mortara Surveyor for Electrocardiographs

A Mortara Surveyor will be used to collect ECG information (in triplicate) at timepoints coinciding with PK Samples. The extracted ECGs will then be blindly reviewed at a later time by an ECG core laboratory reader to determine changes in ECG variables (heart rate, RR, PR, QRS, QT, QTcF and QTcB). Graphical representations between ECG variables (e.g., QTcF) and plasma concentrations of ACER-801 and its metabolite will be generated.

The time and duration of ECG collection must be identical on Day -1, Day 1, and Day 14 and must be planned in relation to predose and 15 hrs postdose PK time points.

11.3.7 Clinical Laboratory Tests

Hematology and coagulation; serum chemistry; urinalysis; urine screening for drugs of abuse, cotinine, and alcohol will be performed for each subject as indicated in Table 1 and [Table 5](#). Clinical laboratory tests may be repeated once for subjects who had previous clinical laboratory test results that revealed clinically significant abnormalities per the investigator's request. Pregnancy tests may be reported in the event of any positive or equivocal test result. If a pregnancy test is positive, Acer must be notified, and the subject will be followed as outlined in [Section 11.2.6](#), until pregnancy outcome. Additional tests may be performed at other times, if deemed necessary. Blood samples may also be used for the assessment of tachykinin peptides, including NKB, NKA, and substance P.

Virology testing will include testing for the presence of HIV antibody, HbsAg, and HCV as indicated in Table 1. Blood samples will be appropriately processed, and laboratory reports will be made available to the investigator in a timely manner to ensure appropriate clinical review and subject inclusion/exclusion based upon results. Procedures for handling and shipping of all laboratory samples will be included in a laboratory manual provided by the central laboratory facility.

All clinical laboratory tests will be performed at the clinical unit) (instructions in the Study Reference Manual and Laboratory Manual).

Abnormalities in clinical laboratory tests that are considered clinically significant by the investigator will be considered Aes and recorded on the AE eCRF. In addition, ALT and AST elevations greater than 5 times the upper limit of normal (i.e., Grade 3 or higher based on CTCAE) will be considered clinically significant for the purposes of this study and reported as Aes.

Any clinically significant abnormal clinical laboratory test results, including test results obtained through Day 16/ET, will be repeated. For any repeat analysis, the abnormal value will be followed regularly until: (1) the value returns to screening or Day -1 values or within normal range; (2) a valid reason, other than Aes related to the study drug, is identified; or (3) the investigator determines that the abnormal value is no longer clinically significant or that further follow-up is no longer deemed medically necessary.

The list of clinical laboratory tests and other analytes to be tested is provided in Table 5.

The total amount of blood taken for the entire study will be approximately 508 mL.

Table 5 List of Clinical Laboratory and Other Analytes to be Tested

Assessment	Analyte
Central Laboratory (Clinical Site)	
Hematology	Hemoglobin, hematocrit, white blood count with differential (neutrophils, lymphocytes, monocytes, eosinophils, basophils), platelet count, red blood cell count (including mean corpuscular volume, mean corpuscular hemoglobin, mean corpuscular hemoglobin concentration)
Coagulation	Prothrombin time, partial thromboplastin time, international normalized ratio
Serum chemistry	Albumin, alkaline phosphatase, total bilirubin, ALT, AST, blood urea nitrogen, calcium, carbon dioxide, chloride, potassium, sodium, total cholesterol, creatinine, gamma glutamyl transferase, glucose, lactate dehydrogenase, phosphorus, total protein, uric acid
Virology	HIV antibody types 1 and 2, HCV antibody, HbsAg
Peptides	Neurokinin B
Hormones	Catecholamines, vasopressin, gonadotropins, estradiol, testosterone, FSH, LH, ACTH, cortisol, TSH, T3 (Total and Free), T4 (Total and Free), prolactin, SHBG, and insulin
Bone Density markers	BSAP, osteocalcin, amino terminal propeptide of type 1 collagen (P1NP) and Collagen Type- C-Telopeptide (CTX)
Urinalysis	pH, specific gravity, protein, glucose, ketones, bilirubin
Drugs of abuse, cotinine, and alcohol	Drugs of abuse including cocaine, amphetamines, barbiturates, opiates, benzodiazepines, cannabinoids, methadone, cotinine (nicotine), and alcohol
Pregnancy test	Serum pregnancy test
COVID-19 screen	As per site policy.
PK Laboratory	
PPD	ACER-801, metabolite

Note: Blood samples may also be used for the assessment of tachykinin peptides, including NKB, NKA, and substance P.

Abbreviations: ACTH = adrenocorticotrophic hormone; ALT = alanine aminotransferase; AST = aspartate aminotransferase; BSAP = Bone specific alkaline phosphatase COVID-19 = coronavirus disease 2019; FSH = follicle stimulating hormone; HbsAG = hepatitis B surface antigen; HCV = hepatitis C virus; HIV = human immunodeficiency virus; LH = luteinizing hormone; PK = pharmacokinetic; SHBG = sex hormone binding globulin; TSH = thyroid-stimulating hormone; T3 = triiodothyronine; T4 = thyroxine.

11.3.8 Analytical Procedures

Whenever possible, all samples from each subject will be analyzed on the same standard curve. Standard and quality control samples will be included in each batch of study samples assayed. Samples with drug concentrations greater than the upper limit of the validated range of the assay will be diluted with the appropriate drug-free biological fluid and re-assayed; those which are below the lower limit of this range will be reported as being below the lower limit of quantification. The analysts will not have access to the randomization scheme.

Analytical results will be presented in tabular form in the final report and chromatographic and derived data will also be provided. Additionally, accuracy, precision, and linearity data for each standard curve and all quality control samples will be presented. Representative chromatograms and standard curve graphs will be included.

12 STATISTICS

The PK, safety, and efficacy data will be presented using descriptive statistics and figures. A statistical analysis plan (SAP), providing details about the specific planned analyses and hypothesis tests will be prepared and approved by Acer and its designees before study database lock and unblinding of subject treatment assignments. An alpha of 0.05 will be used for hypothesis testing with no adjustment for multiplicity.

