3.2 Secondary Objectives

The secondary objectives are to:

- Evaluate the effect of ACER-801 at different doses on the frequency of vasomotor symptoms associated with menopause compared to placebo
- Evaluate the effect of ACER-801 at different doses on the severity of vasomotor symptoms associated with menopause compared to placebo
- Evaluate the effect of ACER-801 at different doses on the hot flash severity score compared to placebo

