4 INVESTIGATIONAL PLAN

4.1 Overall Study Design

This is a Phase 2a, randomized, double-blind, placebo-controlled, dose-ranging study in post-menopausal women in which the pharmacokinetic (PK) profile of ACER-801 at different doses is evaluated and the efficacy of ACER-801 (50 mg twice daily [BID], 100 mg BID, and 200 mg BID) will be compared to placebo in approximately 40 to 56 subjects (approximately 10 to 14 subjects per treatment arm).

Subjects will enter a Screening Period to determine eligibility. Subjects will be required to complete hot flash diaries for 2 weeks prior to randomization. Eligible subjects will be admitted to a Clinical Research Unit (CRU) on Day -1 and remain in the clinic from Day -1 until discharge on Day 16 after completion of treatment and all study assessments or upon withdrawal from the study. The study includes a 14-day safety follow-up assessment (Day 28) ([Figure 1](#)).

Subjects will be randomized in a 1:1:1:1 ratio to ACER-801 per one of the following dosing schedules prior to dosing:

- 50 mg BID
- 100 mg BID,
- 200 mg BID, or
- placebo administered orally for 14 consecutive days (28 doses).

[figure not shown]
Blood samples for PK (plasma) assessment will be collected for concentrations of ACER-801 and its metabolite at predose, 0.5, 1.0, 1.5, 2.0, 2.5, 3.0, 4.0, 5.0, 6.0, 8.0, 12.0 (prior to evening dose), and 15.0 hrs post morning dose on Day 1 and Day 14, as well as predose (prior to morning dose) on Day 2 and Day 7. Plasma samples will also be collected 24 hrs (Day 15) and 48 hrs (Day 16) after the morning dose on Day 14.

Throughout the duration of the study (Day 1 through Day 16), subjects will be required to record the frequency and severity of hot flashes in a subject diary (continuous hot flash diary).

Electrocardiographs using the Mortara Surveyor will be collected on Day -1, Day 1, and Day 14.

During the study, subjects will be closely monitored for safety including assessments of AEs, 12-lead ECGs, atrial oxygen saturation using pulse oximetry, vital signs (sitting and standing blood pressure (BP), heart rate, oral body temperature, and respiratory rate), clinical labs, and physical examinations.

Figure 1 Study Design of ACER-801-201

An overview of the study procedures is presented in Study Duration

This study consists of a 28-day Screening Period, a 14-day Treatment Period, and a 14-day Safety Follow-Up Period.

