12.1 Determination of Sample Size

A sample size of approximately 10 to 14 subjects per arm (approximately 40 to 56 total) is considered sufficient to characterize the PK, safety and preliminary efficacy of ACER-801 based on study results from a dual neurokinin 1,3 receptor antagonists in postmenopausal women (Trower et. al, 2020).

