12.4 Secondary Endpoints

The secondary endpoints are:

- Change in frequency of vasomotor symptoms at Week 1 and Week 2 relative to Baseline
- Change in severity of vasomotor symptoms at Week 1 and Week 2 relative to Baseline
- Change in hot flash severity score at Week 1 and Week 2 relative to Baseline

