12.6.3 Efficacy Analyses

The secondary endpoints are the change in frequency and severity of vasomotor symptoms and hot flash severity score at Week 1 and Week 2 relative to Baseline.

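### Does the lack of a named lead efficacy comparison, with 0.05 tests and no multiplicity adjustment, call for a change to the plan?

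*Combined protocol and SAP*

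**What the plan says.** Section 12 of the protocol sets the testing rule: "An alpha of 0.05 will be used for hypothesis testing with no adjustment for multiplicity". The same paragraph opens by saying that PK, safety and efficacy data will be shown with descriptive statistics and figures. It leaves the detail to an SAP, described in these words: "providing details about the specific planned analyses and hypothesis tests will be prepared and approved by Acer and its designees before study database lock". Treatment assignments are likewise to stay blinded until then. No SAP text is in the supplied document.

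The efficacy objectives in Section 3.2 are secondary and all compare doses with placebo, for example "Evaluate the effect of ACER-801 at different doses on the frequency of vasomotor symptoms associated with menopause compared to placebo". PK and safety are the primary objectives (Section 3.1). Section 12.6.3 contains only the endpoint list: "change in frequency and severity of vasomotor symptoms and hot flash severity score at Week 1 and Week 2 relative to Baseline". It gives no model, test, lead dose, lead endpoint, lead week or testing order. Section 12.1 says the sample size "is considered sufficient to characterize the PK, safety and preliminary efficacy of ACER-801". Section 4.1 describes a "randomized, double-blind, placebo-controlled, dose-ranging study in post-menopausal women", and no dose-trend test is named.

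**The concern.** A plan that will test at 0.05, without adjustment, over several doses, endpoints and weeks, and that marks none of them as leading, leaves room to present the most favourable of many results as if it had been chosen beforehand. With 10 to 14 women per arm, an isolated p<0.05 at one dose and one week is easy to over-read. If all the contrasts were tested, the chance of some false favourable finding would be several times the rate for a single test. The words dose-ranging also raise the question of why no test uses the ordering of the doses.

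**Working it through.** **Inputs from the protocol.** Alpha 0.05 per test, unadjusted (Section 12). Three active doses and placebo, allocated 1:1:1:1 (Sections 4.3 and 6.4). Three efficacy endpoints, each at Weeks 1 and 2 (Section 12.4). 10 to 14 per arm (Section 12.1), which agrees with the stated total: 4 × 10 = 40 and 4 × 14 = 56. The protocol states no power or family-wise error rate, so there is no such figure to reproduce.

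**Assumptions, not in the protocol.** Two-sided tests, normal outcomes, no true effect, and the correlations between endpoints and between weeks.

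**Count.** 3 doses × 3 endpoints × 2 weeks = 18 contrasts.

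**Independence bound.** A two-sided 0.05 test gives a false result in the drug's favour with probability 0.025. Over 18 independent tests, 1 − 0.975^18 = 36.6%. In either direction, 1 − 0.95^18 = 60.3%.

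**Allowing for correlation.** The contrasts share a placebo arm and the endpoints overlap, so independence overstates the rate. Trials were simulated under the null with 4 arms, n = 10 and 14, and t tests using two-arm and four-arm pooled variance. The proportion with at least one of the 18 contrasts significant was:

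| Endpoint / week correlation | In the drug's favour | Either direction |
|---|---|---|
| 0 / 0.5 | 30% | 52-53% |
| 0.3 / 0.7 | 25% | 47-48% |
| 0.5 / 0.7 | 23-24% | 44-45% |
| 0.7 / 0.7 | 20-21% | 39-40% |
| 0.8 / 0.9 | 16% | 31-32% |
| 0.9 / 0.9 | 14% | 27-28% |
| near-perfect | about 6% | 12-13% |

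Other runs at 0.8 / 0.9 gave values down to 15.5%, so 15-25% is a fair range for correlations from 0.3 / 0.7 to 0.8 / 0.9. Sample size and choice of variance matter little. If the 0.05 were one-sided, the figure would be 27-38% at a common correlation of 0.8 to 0.5, against 5% for a single test.

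**Fewer tests.** One endpoint at one week with all three doses: about 6%. One pre-named dose, endpoint and week: 2.5%.

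**What naming a lead would change.** The lead comparison would carry 2.5%. The other 17 contrasts would still be computed and reported, so the chance that some contrast among the 18 is falsely favourable stays where it is in the table. The gain is in the label and in what may be claimed.

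**What a dose-trend lead would change.** Take n = 12 per arm, an assumed maximum effect of 1 SD, four-arm pooled variance (44 df) and trend coefficients c = (−1.5, −0.5, 0.5, 1.5), with Σc² = 5. The noncentrality is Σcμ / √(5/12) for the trend and δ / √(2/12) for one dose against placebo. A single dose with δ = 1 has 1 / 0.408 = 2.45, power 0.67.

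| True means, placebo/50/100/200 mg | Σcμ | Trend noncentrality | Trend power | 200 mg power |
|---|---|---|---|---|
| 0/0.25/0.5/1 (linear in dose) | 1.625 | 2.52 | 0.69 | 0.67 |
| 0/1/1/1 | 1.5 | 2.32 | 0.62 | 0.67 |
| 0/0.5/1/0.5 | 1.0 | 1.55 | 0.33 | 0.22 |
| 0/1/1/0.5 | 0.75 | 1.16 | 0.21 | 0.22 |

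In the last two rows a dose with the full effect would have 0.67, but only if it had been picked in advance. The trend gains 2 points if the response is linear, loses 5 on a plateau, and has low power if the response turns down. No choice of lead is better throughout.

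**The case for a change.** The strongest case for a change is that it costs only wording. Section 12 does commit to hypothesis testing, and the descriptive sentence does not cancel that. Section 12 gives the SAP a deadline but does not require it to name a lead comparison. Declaring that nothing is adjusted does not tell a reader which result was chosen in advance. The count of 18 may even be low, since Section 12.2 defines both mITT and Per-Protocol populations and makes neither the main one for efficacy. Every correlation considered leaves the any-of-18 rate at more than twice the single-test rate.

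Much of this stands. The protocol ranks nothing, the arithmetic is right, and marking one comparison before unblinding is good practice. It does not amount to a needed change, for three reasons. First, the protocol already assigns the tests to a document due before lock and unblinding, which is where and when a lead comparison would be named; whether that document names one cannot be checked here. Second, nothing says all 18 contrasts will be tested, and 15-25% against 2.5% sets any of 18 tests beside one, a gap that naming a lead does not close. Third, unadjusted p-values are acceptable for a secondary objective described as preliminary, and a reader told that there is no adjustment already knows to treat them as nominal. The absence of a trend test is a matter of preference: its power depends on an unknown dose-response shape, and Sections 10.2 and 12.5.6 already plan exposure-response assessment of efficacy.

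**Conclusion.** No change is needed. The protocol leaves unranked up to 18 secondary efficacy contrasts at an unadjusted 0.05. If all were tested two-sided with no true effect, the chance of at least one false favourable result would be about 15-25% at moderate to high correlations, with outer limits of about 6% (near-perfect correlation) and 37% (independence), against 2.5% for one named comparison. These figures rest on correlations and a two-sidedness that the protocol does not state, and on all 18 being tested. This is missing detail that analysts can sensibly fill in the SAP, within a timetable the protocol already sets. PK and safety are primary, and openly unadjusted efficacy results from a Phase 2a trial of this size remain sound as preliminary evidence. An SAP that named one lead endpoint, week and comparison and called the other p-values nominal would read more clearly, but the conclusions the trial can support do not depend on it.
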